3.9.2 Laboratory data

On analyzing laboratory data, data from all sources (central and local laboratories) will be combined. The summaries will include all laboratory assessments collected no later than 30 days after the last administration of study treatment. All laboratory assessments will be listed and those collected later than 30 days after the last treatment date will be flagged in the listings.

Laboratory data will be classified (by biostatistics/statistical programming) into CTC grades according to the NCI Common Terminology Criteria for Adverse Events (CTCAE) v4.03. The calculation of laboratory CTC grades will be based on the observed laboratory values only; clinical assessments will not be taken into account. The criteria to assign CTC grades in this study are given in Appendix 1.

For laboratory tests where grades are not defined by CTCAE, results will be graded by the low/normal/high classifications based on laboratory normal ranges.

The following summaries will be produced for the laboratory data (by laboratory parameter):

- Box plots of laboratory values by scheduled time point and treatment arm.

- Number and percentage of patients with each CTC grade as their worst post-baseline value (regardless of the baseline status). Each patient will be counted only for the worst grade observed post baseline.
- Shift tables using CTC grades to compare baseline to the worst post-baseline value will be produced for hematology and biochemistry laboratory parameters with CTC grades.
- For laboratory parameters where CTC grades are not defined, shift tables to the worst post-baseline value will be produced using the low/normal/high classifications based on laboratory reference ranges.

Number and percentage of patients meeting categorical liver function test criteria, including ALT, AST and ALT/AST (>3x, 5x, 8x, 10x, 20x ULN), Total Bilirubin (>1x, 2x ULN), ALP (>1.5x, 2x, 3x, 5x, 8x, 10x ULN), combined categories of ALT/AST and total bilirubin (e.g., ALT/AST>3x UNL & total bilirubin > ULN) as well as Hy's Law criteria (ALT or AST > 3 x ULN and TBIL \geq 2 x ULN and ALP < 2 x ULN). For the combined categories, the assessments need not to be concurrent, i.e. patients are counted based on their most extreme value for each parameter (highest in the case of ALT, AST and TBIL; lowest in the case of ALP). The following listings will be produced for the laboratory data:

- Listing of patients with CTC grade 3 or 4 laboratory abnormalities;
- Listing of all laboratory data with values flagged to show the corresponding CTC grades and the classifications relative to the laboratory reference ranges.

Time to first occurrence of grade 2 or worse laboratory toxicity and time to first occurrence of grade 3 or worse laboratory toxicity will be summarized for neutrophil, and ALT/AST, using the Kaplan-Meier method. Median time to first occurrence and 95% CI will be provided. In addition, Kaplan-Meier plots will be generated. Simple descriptive statistics, median, min and max as well as 25th percentile and 75th percentile, will be presented.

Time to first occurrence of grade X or worse laboratory toxicity is defined as the time from the start of treatment to the start date of the first incidence of grade X or worse laboratory toxicity, i.e. time in days is calculated as (start date of first occurrence) – (date of first dose of study treatment) +1. A patient will be censored if:

- The patient did not report any post-baseline grade X or worse event on or before the analysis cut-off date.
- The patient discontinued treatment without reporting any grade X or worse event up to 30 days after study treatment discontinuation.
- The patient died without reporting any grade X or worse event.
- The patient received a new anticancer therapy before reporting any grade X or worse event.

The censoring date will be the earliest of the following dates: end of treatment + 30 days, analysis cut-off, new anti-cancer therapy start date, death date and last non-missing

assessment for the lab parameter. Note that patients who have grade X or worse toxicity at the baseline or missing baseline evaluation will be excluded from this analysis.

Duration of grade X or worse laboratory toxicity (for neutrophil, X=2; for ALT or AST, X=3) may also be summarized. Duration of grade X or worse event is calculated as:

(Date when the grade of the event decreases to below X) – (date of onset of grade X or worse event) + 1

For patients experiencing any grade X or worse event, the duration of the first such event will be summarized using the Kaplan-Meier method. Median duration and 95% CI will be presented. In addition, Kaplan-Meier plots will be generated.

A patient will be censored for the duration of grade X or worse event, if:

- The patient dies without reporting a decrease to below grade X
- The patient receives a new anticancer therapy before reporting a decrease to below grade X
- The patient discontinues from the study treatment without reporting a decrease to below grade X up to 30 days after study treatment discontinuation
- The patient is still ongoing at the analysis cut-off date without reporting a decrease to below grade X

The censoring date is the earliest of the following dates: end of treatment + 30 days, analysis cut-off, new anti-cancer therapy start date, death date and last non-missing assessment for the lab parameter.

In addition, failure curves (ascending Kaplan-Meier curves) for time to first occurrence of AE will be constructed by treatment arm. Median together with 95% confidence interval as well as 25th percentile and 75th percentile will be presented for each treatment arm.

3.9.3 Vital signs

Vital signs assessments are performed in order to characterize basic body function. The parameters expected to be collected include: height, weight, body temperature, heart rate, and systolic and diastolic blood pressure.

The criteria for clinically notable abnormalities are defined as follows:

Clinically notable elevated values

- Systolic BP: ≥ 180 mmHg and an increase ≥ 20 mmHg from baseline
- Diastolic BP: ≥ 105 mmHg and an increase ≥ 15 mmHg from baseline.
- Body temperature: $\geq 39.1^{\circ}\text{C}$
- Heart rate: ≥ 120 bpm with increase from baseline of ≥ 15 bpm

Clinically notable below normal values

- Systolic BP: ≤ 90 mmHg and a decrease ≥ 20 mmHg from baseline
- Diastolic BP: ≤ 50 mmHg and a decrease ≥ 15 mmHg from baseline
- Body temperature: $\leq 35^{\circ}\text{C}$
- Heart rate: ≤ 50 bpm with decrease from baseline of ≥ 15 bpm

The following summaries will be produced for each vital sign parameter:

- Summary statistic for change from baseline to the worst post-baseline value (in both directions, i.e. from baseline to highest post baseline and from baseline to lowest post baseline value).
- Number and percentage of patients with at least one post-baseline vital sign abnormality (in both directions, i.e. both elevated and below normal values).

In addition, the following two listings will be produced by treatment arm:

- Patients with clinically notable vital sign abnormalities.
- All vital sign assessments will be listed by patient and vital sign parameter.

In both listings, the clinically notable values will be flagged and also the assessments collected later than 30 days after the last treatment date will be flagged.

3.9.4 ECG

All analyses of ECG data will be based on the average of all available replicate ECGs at each time point for each patient. For unscheduled assessments, 15-minute windows will be applied to group assessments for averaging.

ECG data will be summarized by presenting summary statistics of the raw data and change from baseline by treatment arm and time point. The following parameters will be assessed: QT, QTcF, QTcB, PR, and QRS intervals in msec, heart rate (bpm), and the overall interpretation if clinically significant abnormalities are present.

- The number and percentage of patients with notable abnormalities will be summarized.
- Summary statistics and shift tables will be presented.
- Individual listings will be provided by subject.

Table 3-6 Clinically notable ECG values

ECG parameter (unit)	Clinically notable criteria
	New > 450
	New > 480
QT, QTcF, QTcB (ms)	New > 500
	Increase from Baseline > 30
	Increase from Baseline > 60
PR duration (ms)	Increase > 25% from baseline and to PR duration > 200, New >200
QRS duration (ms)	Increase > 25% from baseline and to QRS duration > 110, New >110
Heart Rate (bpm)	< 50 and decrease from Baseline of > 25%

> 100 and increase from Baseline of > 25%

A newly occurring ECG abnormality is defined as an abnormal post-baseline ECG finding that is not present at Baseline. Baseline is defined as the average of the last ECG measurements (replicates taken on or before date of first dose of study treatment. The percentage of patients having notable ECG interval values is based on the number of patients at risk for the change with a value at baseline and post-baseline.

Time to grade 2 or worse QTcF prolongation will be analyzed using the Kaplan-Meier method and the median time to grade 2 or worse QTcF prolongation will be presented along with a 95% confidence interval if there are sufficient events for each treatment group. Simple descriptive statistics, median, min and max as well as 25th percentile and 75th percentile, will be presented. Note that patients who have grade 2 or worse toxicity at the baseline or missing baseline evaluation will be excluded from this analysis.

3.9.5 Cardiac imaging (MUGA / ECHO)

Shift tables comparing baseline to worst post-baseline cardiac imaging (MUGA or ECHO) overall interpretation will be provided. Percentages will be based on all patients in the Safety set.

Note: If there is any change in the methodology used throughout the study compared to baseline, the post-baseline values for which the methodology differs from baseline will be discarded in the tables presenting comparisons to baseline.

Descriptive statistics of the left ventricular ejection fraction (LVEF) at baseline, worst post-baseline value and change from baseline to worst post-baseline value will be provided.

A listing of patients with newly occurring clinically significant abnormality will be produced by treatment arm.

3.9.6 Urinary Analysis

The following parameter will be summarized using shift table to compare baseline to the worst-post baseline values: urine bilirubin dipstick, urine blood dipstick, urine glucose dipstick, urine ketones dipstick, urine leukocyte dipstick, and urine nitrate dipstick. For all these parameters, both negative and trace are considered as normal and the more pluses the worse. The urine pH dipstick will be summarized using shift table with low/normal/high classifications based on laboratory reference ranges.

3.9.7 Other safety data

Data from other tests will be listed, notable values will be flagged, and any other information collected will be listed as appropriate.

All assessments collected later than 30 days after the last treatment date will be flagged in the listings.

Any statistical tests performed to explore the data will be used only to identify any interesting comparisons that may warrant further consideration.

Subgroup analyses will be explored as described in [Section 3.14.1](#).

3.10 Pharmacokinetic (PK) analyses

3.10.1 General principle

All PK analyses will be based on PAS set, unless otherwise specified.

Evaluable pre-dose concentrations satisfy the below conditions:

- Sample was collected before the current dose
- In addition, for pre-dose concentrations collected on Day 15 of any cycle
 - Patient had at least 10 consecutive days of ribociclib dosing (either 10 doses at 600 mg or 10 doses at 400 mg or 10 doses at 200 mg) immediately prior to the pre-dose collection. Ten consecutive doses are expected to provide adequate time to reach steady state for ribociclib at 600 mg and after dose reduction.
 - The PK collection was done at 24 ± 2 hours after the previous dose on Day 14 of the corresponding cycle.
 - Patient did not vomit within the first 4 hours following the last dose (confirmed using the records of date/time of PK sample collection and dosing).
 - the concentration has not been flagged for exclusion by the pharmacokineticist

Evaluable post dose 2h, 4h, 6h concentrations on Day 15 of any cycle satisfy the below conditions:

- Patient had at least 10 consecutive days of ribociclib dosing (either 10 doses at 600 mg or 10 doses at 400 mg or 10 doses at 200 mg) immediately prior to the PK collection.
- The PK collection was done within ± 15 minutes window of 2 hours after the Day 15 dosing for the post 2h concentration
- The PK collection was done within ± 30 minutes window of 4, 6 hours after the Day 15 dosing
- Patient did not vomit within the first 4 hours following the current dose.
- the concentration has not been flagged for exclusion by the pharmacokineticist

Only evaluable PK concentrations which are not flagged for exclusion will be used for figures, summaries, and statistical analysis. Concentration listings will include all concentrations, with flags indicating those excluded from analyses.

3.10.2 PK concentrations

PK concentrations of ribociclib and LEQ803 at C2D1 will be summarized for fulvestrant+ ribociclib arm.

In addition, ribociclib and LEQ803 steady state concentrations (i.e., Cycle 1 Day 15 and Cycle 2 Day 15 concentrations) will be also summarized by ribociclib dose level, visit, and timepoint. Patients will be classified into the following dose groups at each visit (C1D15 and C2D15) and timepoint:

- RIBO600: consists of all patients who provided evaluable concentrations after receiving at least 10 consecutive daily ribociclib doses of 600 mg immediately prior to the PK collection without a dose change or interruption.
- RIBO400: consists of all patients who provided evaluable concentrations after receiving at least 10 consecutive daily ribociclib doses of 400 mg immediately prior to the PK collection without a dose change or interruption.
- RIBO200: consists of all patients who provided evaluable concentrations after receiving at least 10 consecutive daily ribociclib doses of 200 mg immediately prior to the PK collection without a dose change or interruption.

Additional separate summaries of ribociclib and LEQ803 will be produced for Asian and non-Asian patients (based on race) at each visit (C1D15 and C2D15) by ribociclib dose level and timepoint.

Descriptive statistics of concentrations will include n, m (number of non-zero concentrations), mean, CV%, SD, median, geometric mean, geometric CV%, minimum and maximum). Coefficient of variation CV% is calculated as below:

$$100 \cdot (\text{SD} / \text{arithmetic mean})$$

Geometric CV% is calculated as follows from non-zero values:

$$CV(\%) = 100 \cdot \sqrt{\exp(\hat{\sigma}^2) - 1}$$

where $\hat{\sigma}^2$ denotes the variance of the log-transformed values.

All individual plasma ribociclib (and also LEQ803) concentration data will be listed for fulvestrant + ribociclib arm using the Full analysis set. The meal record will be listed using Full Analysis Set.

3.10.3 Analysis of relationship between efficacy or safety endpoints and exposure

3.10.3.1 Exposure vs. PFS and TTR

The relationship between ribociclib exposure and PFS/TTR will be explored using the Kaplan-Meier method. Kaplan-Meier plots of the distribution of PFS and TTR by category of average Ctrough at steady state (denoted as Ctrough_avg_ss) will be presented, along with the median time for each category if estimable. For each patient, Ctrough_avg_ss will be calculated as the geometric mean of evaluable Ctrough values from C1D15 and C2D15. For the patients with only one evaluable Ctrough, the Ctrough_avg_ss will be that evaluable Ctrough itself. The Ctrough_avg_ss categories are defined as follows: < 25%, 25% to < 50%, 50% to < 75%, and \geq 75%. The data will be analyzed using PAS.

3.10.3.2 Exposure vs. QTcF

The relationship between ribociclib concentration and the mean change from baseline QTcF (i.e., Δ QTcF) will be explored graphically: the arithmetic mean Δ QTcF and geo-metric mean ribociclib concentration will be displayed together against nominal time (time in x-axis, Δ QTcF and concentration in y-axis) using the PAS. The mean will be taken with respect to all the measurements from all patients at the same given nominal time. If a patient does not have both QTcF and evaluable PK measurement at a certain time point, then this patient will not be included in the plot for that time point.

In addition, the relationship between ribociclib dose level and QTcF will also be explored using the safety set. Patients will be classified into the following dose groups at each scheduled QTcF collection time point on C1D15 and C2D15.

- RIBO600: consists of all patients who received at least 10 consecutive daily ribociclib doses of 600 mg without a dose change or interruption immediately prior to the corresponding QTcF collection timepoint.
- RIBO400: consists of all patients who received at least 10 consecutive daily ribociclib doses of 400 mg without a dose change or interruption immediately prior to the corresponding QTcF collection timepoint.
- RIBO200: consists of all patients who received at least 10 consecutive daily ribociclib doses of 200 mg without a dose change or interruption immediately prior to the corresponding QTcF collection timepoint.

Summary statistics of the raw QTcF data and change from baseline will be presented by visit, time point and dose group using the safety set. Only scheduled QTcF on C1D15 and C2D15 will be included in the analysis.

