### Amendment rationale

Study CLEE011F2301 was initiated in June 2015 and enrollment is currently ongoing.

As of February 17th 2016, 351 patients have been randomized in the study.

The purpose of this amendment is to:

**(i) Update and clarify the safety monitoring of patients to be consistent across ribociclib clinical trials, and better characterize the QTc and liver side effects, including:**

- Management of QTcF prolongation:

Potential risk of QT prolongation has been observed in patients treated with ribociclib. Updates to inclusion and exclusion criteria, ECG monitoring (triplicates) and dose modification guidelines for QTcF prolongation have been made.

- Management of hepatic toxicities:

Recent data suggests a potential risk of hepatic toxicity (drug induced liver injury [DILI] indicated by an increase of transaminases, in isolation or with bilirubin increase) in patients treated with ribociclib. Updates to monitoring and dose adjustment guidelines for hepatobiliary toxicities including ALT, AST and total bilirubin have been added and separated from the dose modification guidance for other adverse events.

- Management of dose modification based on local laboratory results:

Clarification was provided that, in case of safety emergency, local laboratories results can be used to evaluate the need for potential study treatment dose modifications.

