### 7.2.3 Pharmacokinetics

**Following protocol amendment 4, there will be no more PK blood collection, including patients that cross-over to the LEE011 combination arm.**

Pharmacokinetic blood samples will be obtained from all patients for the analysis of ribociclib (and any relevant metabolites such as LEQ803). Patients will be assigned to the sparse PK collection group or the trough PK collection group.

- Sparse PK collection group: In the sparse PK group, approximately the first 150 patients enrolled will have PK collections as described in [Table 7-6](#).

- Trough PK collection group: In all remaining patients, PK collections will be collected as described in [Table 7-7](#).

Meal conditions (fasting, low fat, high fat) will be recorded within  $\pm$  30 minutes of a dose on the meal record eCRF page for patients assigned to the sparse PK collection group on Cycle 1 Day 15 and Cycle 2 Day 15; the impact of meal conditions on PK in patients may be explored. Refer to [Section 6.1.1.2](#) and [Section 10.6.3](#) for details.

An unscheduled PK blood sample may be collected at any time for measurement of plasma drug concentrations if clinically indicated or at the Investigator's discretion. If a patient discontinues from the study treatment due to toxicities related to study treatment, an unscheduled PK blood sample may be obtained as soon as possible after the last dose and the date and time of last dose recorded. In addition, an unscheduled blood sample may be collected if additional ECG measurements are conducted.

The date and exact time of dosing on PK collection days, as well as the date and actual time of blood sampling must be recorded on the appropriate eCRF pages. In addition, the exact time of dosing on the previous day must be precisely recorded.

If vomiting occurs during the course of treatment, no re-dosing of the patient is allowed, and medication should resume on the next day. The occurrence and frequency of any vomiting must be noted in the adverse events section of the eCRF. In addition, the date and exact time of vomiting should only be recorded if it occurs within 4 hours of dosing on the days of PK sampling. If a vomiting episode occurs within the first 4 hours post-dosing during the day of the last dose prior to trough PK samples the exact time (whenever possible) must be noted on the eCRF. A detailed description of the planned analyses for PK is given in [Section 10.5.4](#).

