**Table 7-6 Sparse pharmacokinetic blood collection log**

Note: Sparse PK sampling will be performed on approximately the first 150 patients in this study. Blood for Sparse PK profiling will be collected on C1D15 and C2D15 at Pre-dose (0), 2, 4, 6hr, and C2D1 Pre-dose (0hr) for ribociclib/placebo. Only for the sparse PK group, the meal condition (fasting, low fat, high fat) will be collected within ± 30 minutes of the dose on the eCRF on days C1D15 and C2D15.					
Cycle	Day	Scheduled Time Point Relative to Dosing	DRID No. for ribociclib/placebo	PK Sample No. for ribociclib/placebo	Blood Volume (mL)
1	15	Pre-dose a	101/1001 d	101	3
		2h post-dose (± 15 min)	101	102	3
		4h post-dose (± 15 min)	101	103	3
		6h post-dose (± 15 min)	101	104	3
2	1	Pre-dose a	102	105	3
	15	Pre-dose a	103/1003 d	106	3
		2h post-dose (± 15 min)	103	107	3
		4h post-dose (± 15 min)	103	108	3
Unscheduled		Anytime b	NA	1001+	3
		PK samples related to a QTcF ≥ 501 ms c	NA	1051+	3

a. Collect Pre-dose PK sample immediately before drug administration (approximately 24-hrs after the last dose and immediately before the next dose)

b. Unscheduled PK blood samples may be collected at any time for measurement of plasma drug concentrations if clinically indicated or at the Investigator's discretion and will be uniquely, sequentially numbered 1001, 1002, etc., for ribociclib/placebo

c. Unscheduled PK samples related to a QTcF ≥ 501 ms will be uniquely, sequentially numbered 1051, 1052, etc., ribociclib/placebo

d. The first dose reference ID (DRID) No. is for the current dose, while the second DRID No. is for the last dose the subject received prior to the collection of the PK sample

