**Table 7-7 Trough pharmacokinetic blood collection log**

Note: Trough PK sampling will be performed in all remaining patients Pre-dose on C1D15, C2D1 and C2D15.					
Cycle	Day	Scheduled Time Point Relative to Dosing	DRID No. for ribociclib/placebo	PK Sample No. for ribociclib/placebo	Blood Volume (mL)
1	15	Pre-dose a	201/2001 d	201	3
2	1	Pre-dose a	202	202	3
	15	Pre-dose a	203/2003 d	203	3
Unscheduled		Anytime b	NA	2001+	3
		PK samples related to a QTcF ≥ 501ms c	NA	2051+	3

a. Collect Pre-dose PK sample immediately before drug administration (approximately 24-hrs after the last dose and immediately before the next dose)

b. Unscheduled PK blood samples may be collected at any time for measurement of plasma drug concentrations if clinically indicated or at the Investigator's discretion and will be uniquely, sequentially numbered 2001, 2002, etc., for ribociclib/placebo

c. Unscheduled PK samples related to a QTcF ≥ 501 ms will be uniquely, sequentially numbered 2051, 2052, etc., ribociclib/placebo

d. The first DRID No is for the current dose, while the second DRID No is for the last dose the subject received prior to the collection of the PK sample

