2.3.4 Pharmacokinetic analysis set

The Pharmacokinetic analysis set (PAS) consists of all patients who provide at least one evaluable PK concentration (see [Section 3.10.1](#) for definition of evaluable PK concentration).

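### The exploratory exposure–QTcF plot averages up to about 485 ribociclib patients at pre-dose but only about 100 at 2 h and 4 h, so its within-day course is not drawn on the same patients

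*SAP*

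**What the plan says.** Section 3.10.3.2 of the SAP for the primary PFS analysis displays arithmetic mean change from baseline in QTcF together with geometric mean ribociclib concentration against nominal time. The averaging rule is "The mean will be taken with respect to all the measurements from all patients at the same given nominal time". The pairing rule is "If a patient does not have both QTcF and evaluable PK measurement at a certain time point, then this patient will not be included", and that exclusion applies only at the time point concerned. The analysis set is broad (section 2.3.4): "The Pharmacokinetic analysis set (PAS) consists of all patients who provide at least one evaluable PK concentration". It therefore holds both PK sampling groups.

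The protocol defines those groups in section 7.2.3 by order of entry: "approximately the first 150 patients enrolled will have PK collections" on the sparse schedule. Table 7-6 gives that schedule: "Blood for Sparse PK profiling will be collected on C1D15 and C2D15 at Pre-dose (0), 2, 4, 6hr". Table 7-7 covers everyone else: "Trough PK sampling will be performed in all remaining patients Pre-dose on C1D15, C2D1 and C2D15".

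ECGs do not depend on PK group. Protocol Table 7-5a schedules them for all patients at pre-dose, 2 h and 4 h on C1D15, and at pre-dose and 2 h on C2D15.

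**The concern.** The pairing rule makes QTcF and concentration comparable at any one time point, because both come from the same patients there. The figure, however, is read across time points: does QTcF rise and fall with concentration through the dosing day? For that reading the patients behind successive points need to be the same, and here they are not. Trough-only patients enter at pre-dose and then disappear.

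The contrast affected is the one of most interest. Protocol section 1.2.1.2.1 links QT changes to maximum drug levels between 1 and 8 h after dosing, and section 1.2.1.2.3 gives a median Tmax of 2.1 h at 600 mg. If sparse and trough-only patients differ in mean change in QTcF or in trough concentration, part of the plotted step from pre-dose to 2 h reflects who is being averaged. Sparse status follows enrolment order rather than random selection, so equality of the two groups is not guaranteed by design.

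**Working it through.** **Inputs**
- Sparse PK group: about 150 patients (protocol 7.2.3 and Table 7-6).
- Allocation 2:1 and planned N = 660 (SAP 1.1).
- Randomized N = 727 (protocol, Amendment 2 rationale). An exact 2:1 split of the 727 is assumed.

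**The plan's own figure.** SAP 3.18 expects sparse ribociclib concentrations in approximately 100 patients: 150 × 2/3 = 100. This reproduces.

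**Who can enter each point.** A patient needs a scheduled ECG and a scheduled PK sample at that time.

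| Time | ECG | PK | Ribociclib patients who can enter |
|---|---|---|---|
| Pre-dose, C1D15 and C2D15 | all | sparse and trough-only | 440 (N = 660) or about 485 (N = 727) |
| 2 h, C1D15 and C2D15 | all | sparse only | about 100 |
| 4 h, C1D15 | all | sparse only | about 100 |
| 4 h, C2D15 | none scheduled | sparse only | 0 |
| 6 h | none scheduled | sparse only | 0 |

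The pre-dose counts are 660 × 2/3 = 440 and 727 × 2/3 = 484.7. They are ceilings, since only patients with a paired QTcF and an evaluable trough count. The sparse patients are a subset of the pre-dose group, not a separate sample.

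**Share of the pre-dose mean that cannot appear after dosing**
- N = 660: (440 − 100)/440 = 340/440 = 77.3%.
- N = 727: (484.7 − 100)/484.7 = 384.7/484.7 = 79.4%.

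If the evaluable fraction is the same in both groups, the counts shrink but the shares do not. At an assumed 60% to 80% evaluable with N = 660, the counts are 264 to 352 against 60 to 80. If evaluability differs between groups (assumed 90% against 60%, either way round, N = 660):
- Sparse 90%, trough-only 60%: sparse share 90/(90 + 204) = 31%, so trough-only 69%.
- Sparse 60%, trough-only 90%: sparse share 60/(60 + 306) = 16%, so trough-only 84%.

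**What that does to the plotted change.** Let S and T be the mean pre-dose change in QTcF in sparse and trough-only patients, w the trough-only share, and S2 the sparse mean at 2 h.
- Plotted pre-dose mean = S + w(T − S).
- Plotted change to 2 h = (S2 − S) − w(T − S).

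The first term is the within-patient change wanted, provided the same sparse patients supply both points. The second is a composition term: w, about 0.77 to 0.79, times whatever the group difference T − S happens to be. The same holds for geometric mean concentration on the log scale. On a common set of patients w = 0 and the term vanishes. The documents give no value for T − S.

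**A smaller mismatch within the sparse group.** Under SAP 3.10.1, a Day 15 pre-dose sample must fall 24 ± 2 h after the previous dose to be evaluable; the post-dose conditions do not list that requirement. A sparse patient can therefore enter at 2 h without entering at pre-dose.

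**The case against.** The strongest reply is that the plan does not rely on this figure. The second half of 3.10.3.2 summarizes raw QTcF and change from baseline by visit, time point and dose group in the safety set, with no PK sample required. Section 3.9.4 adds ECG summaries by arm and time point, notable QTcF categories and time to grade 2 or worse QTcF prolongation. A reader who doubts the plot can check it against these. The figure is also exploratory, with no test or decision rule attached, and the figure shells are not in the documents, so n per time point may already be planned. All of this stands, and it limits how much the point matters.

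Plotting change from each patient's own baseline also removes stable differences in QTcF level between the groups. That is true, but it does not remove a difference in exposure or in response to the drug.

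A reader might go further and infer that the two groups differ systematically, because the sparse patients all came in before Amendment 1, which revised QT-related eligibility and ECG monitoring. The protocol does record "As of February 17th 2016, 351 patients have been randomized in the study", so the first 150 predate it. But no document reports QTcF by enrolment period, and the amendment does not coincide with the sparse/trough split. At least 351 − 150 = 201 of the 727 − 150 = 577 other patients (35%) were also randomized before that date. At most 727 − 351 = 376, or 52% of all randomized, came after it. Nor can a size in milliseconds be attached, since any such figure would rest wholly on an assumed group difference.

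A reader might also fault the plot for having no placebo curve. Placebo patients have no ribociclib concentration to pair, and placebo change from baseline by time point is already planned in 3.9.4. An overlay would be a preference, not the repair of a defect.

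**Conclusion.** The point holds as a minor one. Applied literally, 3.10.3.2 produces a within-day curve whose pre-dose point can rest on up to about 440 to 485 ribociclib patients and whose 2 h and 4 h points can rest on about 100. With equal evaluability, 77% to 79% of the pre-dose patients cannot contribute after dosing; under the unequal evaluability assumed above, the range is 69% to 84%. Any difference between sparse and trough-only patients would carry into the plotted change in that proportion.

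This rests on the sampling schedules, an exact 2:1 split and the averaging rule as worded. It does not rest on, and does not establish, an actual difference between the groups: size and sign are unknown. Nor does it mean that the plan as a whole could miss a within-day QTcF rise, because the summaries that need no PK sample are unaffected.

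**What to change.** In SAP 3.10.3.2, draw the within-day curve separately for C1D15 and C2D15, using only patients with paired QTcF and evaluable PK at every plotted time of that visit: pre-dose, 2 h and 4 h on C1D15; pre-dose and 2 h on C2D15. Show the trough-only patients' pre-dose mean as a separate symbol, and print n at each time point. Stating that the visits are kept apart also settles a matter the SAP leaves open. Pooling them by nominal time would change the composition again at 4 h, where only C1D15 has an ECG.

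No new data are needed: the change is to the SAP wording and the figure specification, and a figure already produced can be redrawn from the data held. The cost is that the pre-dose point of the curve rests on about 100 patients at most, with the remaining troughs shown beside it.
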